if applying TMS to the left hemisphere of the brain, a twitch will be observed in the right hand). This is referred to as the resting motor threshold (RMT). In both cases, the scalp region producing the largest hand twitch will be identified. To identify this region, TMS will be set to 30% of the maximal stimulator output, which is well below the motor threshold for most, if not all, individuals. TMS will be delivered to a scalp location approximating the location of motor cortex based upon surface features using the nose and ears as landmarks. From this initial location, TMS will be delivered. If ineffective to produce a hand twitch, the TMS coil will be moved to a new, nearby site, which will subsequently be tested. This process will continue until a grid of locations has been tested around the starting location, approximating 5 cm^2. If a hand twitch has not been produced, this indicates that the stimulation is below threshold and the stimulator output will be raised by 5% of the maximum stimulator output. The process will then repeat until the maximal hand twitch at a given stimulation level is observed, thereby indicating the location of interest. During this process, the participant will be closely monitored and periodically asked whether the stimulation is producing any discomfort or unusual symptoms (e.g. dizziness). At the scalp location of interest, the lowest TMS intensity able to elicit 5 visible cessations of EMG activity in 10 trials (AMT), or 5 visible twitches in 10 trials (RMT) at this site will be determined. Individual MT will be used to determine the intensity of stimulation for each individual, as recommended by safety guidelines. This procedure usually takes about 5 minutes and also serves the purpose of acquainting participants to TMS stimulation. Once MT is determined, TMS will be administered within the limits of the safety guidelines recently updated in Rossi et al., 2021. An additional 12 years of research using TBS ranging between 80% and 100% RMT was examined to determine the continued efficacy of previously established guidelines in Rossi et al., 2009. Since the 2009 publication, the scientific community has gained a better understanding of safety risks and the rarity of adverse events (such as seizure) associated with TMS. To reflect current safety guidelines for offline studies using TBS, TMS will never exceed 100% of RMT or 120% of AMT.

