  - a. The WHODAS is a generic assessment instrument developed by WHO to provide a standardized method for measuring health and disabilities across cultures.
- Patient Health Questionnaire (PHQ-9)
  - a. The PHQ-9 is a brief depression severity measure.
- Generalized Anxiety Disorder (GAD-7)
  - a. The GAD-7 is a brief measure for assessing generalized anxiety disorder.
- Quick Inventory of Depressive Symptomatology (QIDS-SR)
  - a. The QIDS-SR is a brief self-report assessment of depressive symptoms.
- Pain scale
  - a. Self-reported pain scale.
- Depression Anxiety and Stress Scale (DASS 21)
  - a. a 21-item questionnaire to assess symptoms of depression, anxiety and stress.

  

- Interviews
  - Montgomery-Asperg Depression Rating Scale (MADRS)
    - a. The MADRS is a diagnostic questionnaire to measure the severity of depressive episodes.

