PROTOCOL TITLE:

risks and exclude participants accordingly. See section 15.1 for further details of seizure risks.

Personnel who administer TMS will be trained to recognize a potential seizure event and to act as first responders in order to administer appropriate initial care. In addition, all study personnel will be trained in Basic Life Support and CPR usage. However, we wish to emphasize that there are no known cases where individuals required the use of CPR during a TMS session. The major physical signs the study personnel will look out for in detecting a potential seizure include chewing movements, convulsions/tremor/shaking, difficulty talking, a blank stare, eyes rolling up, and profuse sweating. If any of these signs are observed, study personnel will stop the research procedure and inquire whether the subject feels okay. If the subject is unresponsive (and therefore likely experiencing a seizure), first-aid will be supplied. The first-aid response consists of making sure the subject is physically safe for the duration of the seizure. This involves moving the subjects out of the TMS chair and onto the floor lying down on their left side. The subject will be kept lying down on their left side, while the staff call emergency medical help, via a 911 call. Resources available in the laboratory include a first-aid kit and immediate phone access. In the extremely unlikely event of an actual occurrence of a seizure, it will be immediately reported to the IRB. To minimize headaches and/or other forms of discomfort, the experimenter will encourage participants to report any form of discomfort during the procedure. The experimenter will periodically directly query the participant regarding whether or not they are experiencing discomfort. In addition, an arm will be used to help support the coil to reduce downward pressure on the subject that could lead to neck discomfort. The experimental procedure will be immediately terminated whenever anyone reports experiencing discomfort. To prevent adverse effects on hearing due to the sound produced by TMS, all experimental participants will wear ear plugs.

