## 10.0 Inclusion and Exclusion Criteria\*

### 10.1 Describe how individuals will be screened for eligibility.

Participants will be screened in order to minimize risks associated with TMS and fMRI. Screening will proceed with a combination of e-mail, phone, and in person questions. First, the screening forms will be sent to the participant via e-mail (see Appendix), performed

over the phone, or both. If the participant passes the first phase of screening and remains interested in participating, the participant will be invited to perform the study. Participants will read the consent form and any questions will be answered. Screening for TMS will be completed again in each experimental session to assess if any changes have occurred prior the last screening. The individuals included in this study will be adults from ages 18 to 55.

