Personnel who administer TMS will be trained to recognize a potential seizure event and to act as first responders in order to administer appropriate initial care. In addition, all study personnel will be trained in [Basic Life Support](#) and CPR usage. However, we wish to emphasize that there are no known cases where individuals required the use of CPR during a TMS session. The major physical signs the study personnel will look out for in detecting a potential seizure include chewing movements, convulsions/tremor/shaking, difficulty talking, a blank stare, eyes rolling up, and profuse sweating. If any of these signs are observed, study personnel will stop the research procedure and inquire whether the subject feels okay. If the subject is unresponsive (and therefore likely experiencing a seizure), first-aid will be supplied. The first-aid response consists of making sure the subject is physically safe for the duration of the seizure. This involves moving the subjects out of the TMS chair and onto the floor lying down on their left side. The subject will be kept lying down on their left side, while the staff call emergency medical help, via a 911 call. Resources available in the laboratory include a first-aid kit and immediate phone access. In the extremely unlikely event of an actual occurrence of a seizure, it will be immediately reported to the IRB.

Local pain, headache, or discomfort. The most commonly reported side effect of TMS is headache. This headache is typically of a muscle-tension type. It usually develops during or immediately after the stimulation and may last for minutes to hours following the end of the stimulation. It is typically limited to the day of stimulation. Neck pain or scalp pain may also occur. Both are usually managed easily with over-the-counter analgesics. The experimental procedure will be immediately terminated whenever anyone reports experiencing discomfort. There are no reports of any such effects recurring. For many scalp

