locations, TMS feels only like a sudden tap on the scalp accompanied by a clicking sound. For other scalp locations, TMS can cause face or limb twitches. These twitches are not painful, but can feel odd or disquieting when first experienced. On some occasions, TMS might cross the threshold to the point where it would actually be described as producing a slightly painful scalp sensation. We will closely monitor subjects' comfort and will request them to tell us if the stimulation ever feels painful. If this occurs, we will immediately decrease TMS intensity to a level that is not painful. It is important to note that the likelihood of headache and other discomfort depends upon the stimulation parameters. Parameters for clinical applications for depression note a rate of 28% for pain, which is greater than the 16% observed for sham (i.e. no true stimulation; Loo et al., 2008). However, for TBS, the rate is less than 3% (Oberman et al., 2011). In many cases, discomfort can be due to neck pain resulting from holding one's head still against the coil. The figure 8 coil (MCF-B65) is lightweight compared to most coils and will be supported by an arm for positioning that alleviates downward pressure on the subject. Therefore, we anticipate rates of adverse effects due to pain and discomfort will be low and in accordance with the PI's previous history with the technique.

Transient hearing changes. TMS produces an audible clicking noise when the current passes through the coil. This click can result in tinnitus and transient decreased hearing if no protection is used. To prevent this adverse effect, all experimental participants will wear ear plugs. Animal and human studies have demonstrated that earplugs can effectively prevent the risk of hearing disturbances or discomfort due to TMS. The experimenters will also be provided with ear protection devices to minimize any discomfort they might experience from the clicks.

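### The plan specifies no systematic end-of-session or between-session question on headache, neck or scalp pain, or hearing, so milder symptoms after a TMS visit may be under-counted

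*Combined protocol and SAP*

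**What the plan says.** On the harm, section 15.1 states: "The most commonly reported side effect of TMS is headache". On its timing: "It usually develops during or immediately after the stimulation and may last for minutes to hours following the end of the stimulation". It adds that the headache is usually confined to the day of stimulation and that neck or scalp pain may also occur. On hearing: "This click can result in tinnitus and transient decreased hearing if no protection is used". The stated safeguard is ear plugs for every participant.

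On asking about it, section 6.3 says that "the experimenter will encourage participants to report any form of discomfort during the procedure", and then: "The experimenter will periodically directly query the participant regarding whether or not they are experiencing discomfort". During motor-threshold finding (section 6.1) participants are "periodically asked whether the stimulation is producing any discomfort or unusual symptoms". Section 15.1 also asks them to say if stimulation becomes painful.

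Three other provisions bear on later symptoms:
- Section 6.2 lists an instrument described only as "Self-reported pain scale", with no time point, recall period or body site.
- Section 10.1 says: "Screening for TMS will be completed again in each experimental session to assess if any changes have occurred prior the last screening". Section 10.2 includes severe headaches and tinnitus among the TMS exclusion grounds, and hearing impairment among the other exclusions.
- Section 6.3 commits the investigators to monitoring adverse events, but gives no form, schedule or window.

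Sections 4.2 and 18.1 are both answered NA. The latter is where the method and frequency of safety data collection would be set out.

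**The concern.** The period in which the protocol expects its commonest side effect extends past the period in which it clearly plans to ask about it. A participant whose mild headache starts on the way home and is gone by the evening fits the course described in 15.1, yet meets no scheduled question. The same holds for a brief change in hearing.

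Section 15.1 expects low rates of pain and discomfort and cites under 3% for theta-burst. If later symptoms are recorded only when someone happens to mention them, any rate taken from the study will tend to be too low and will appear to bear out that expectation. This matters more here than in a single-session study, because stimulation is repeated five times within a week in people selected for anhedonia, and tolerability across repeated sessions is something the study is well placed to document.

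**Working it through.** The plan gives no event count or adverse-event rate of its own to reproduce. The check compares the two windows and then sizes the pool of events at stake.

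**Step 1: the windows side by side.**
- Symptom window (15.1): onset during or just after stimulation, lasting minutes to hours, usually within the day.
- Threshold finding (6.1): asked periodically, about the stimulation then being given.
- Procedure (6.3): spontaneous reports during it, plus a periodic query about present discomfort.
- Stimulation (15.1): asked to report if it is painful.
- After stimulation, still on site: tasks follow TMS (15.1), so staff are present, but no query is scheduled at the end of the visit.
- After leaving: nothing is scheduled until the next session's TMS screen, which is an eligibility check.
- Hearing: prevention only. No question about hearing after stimulation is described.

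Section 9.1 puts a session at 30 minutes to 2 hours, so a headache lasting hours can outlast the visit. For a count of events, however, onset matters more than duration. The events at risk of being missed are those that begin after departure, and those that begin on site but are neither volunteered nor asked about.

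**Step 2: what the repeat screen can catch.** Severe headache and persisting tinnitus or hearing impairment correspond to exclusion grounds and could surface at the next session. A mild headache that resolved the same day would not be expected to. Read literally, the sentence in 10.1 looks for changes before the last screening rather than since it. This is probably a slip, but it should be corrected.

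**Step 3: size of the pool.** Inputs: under 3% for theta-burst (15.1, with no statement of whether per person or per session); 80 participants (section 1.0) or 150 (section 12.1); five TMS sessions (section 2.2).

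Per person, ceiling = N × 0.03:
- 80 × 0.03 = 2.4
- 150 × 0.03 = 4.5

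Per session, ceiling = N × sessions × 0.03:
- 80 × 5 = 400 sessions; 400 × 0.03 = 12
- 150 × 5 = 750 sessions; 750 × 0.03 = 22.5

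If each participant had five sessions at each of two sites, which the protocol does not state, 80 participants would give 800 sessions and 800 × 0.03 = 24.

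**Step 4: effect of missing a fraction f.** Recorded events = ceiling × (1 − f). The documents give no value for f, so the range is purely illustrative.
- f = 0.25: 2.4 becomes 1.8; 12 becomes 9
- f = 0.50: 2.4 becomes 1.2; 12 becomes 6
- f = 0.75: 2.4 becomes 0.6; 12 becomes 3

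With so few events, one or two missed reports would change the recorded rate materially, and always downward.

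**The case against.** A reader might infer that discomfort is asked about only while the coil is in use, that ascertainment stops before the headache window opens, and that later headache and hearing change go uncounted altogether. The documents do not support this. Headache usually starts during or just after stimulation, so the windows overlap at the usual onset. Participants stay for the tasks, and 15.1 expects cognitive effects of up to an hour to have worn off before they leave. The periodic query in 6.3 is not expressly limited to time under the coil. A pain scale is listed, and its use after stimulation is neither planned nor ruled out. Adverse events are to be monitored. The screening forms are attachments not reproduced in the text, so their items cannot be checked.

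Nor can it be said that nothing follows the final TMS session. Section 1.0 gives participation of 4 to 5 weeks, section 3.2 asks whether changes last longer, and no visit schedule excludes a later visit with a screen.

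A third tempting inference is that a comparison of tolerability between medial prefrontal and inion stimulation would be distorted. No such comparison, and no adverse-event rate, is planned.

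On size, 15.1 also quotes 28% pain under clinical depression parameters (16% under sham). The protocol sets that figure against theta-burst, so it is not a fair basis for the expected count here. The hearing risk is stated as arising without protection, and all participants wear ear plugs.

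All of this stands. It narrows the point without removing it: none of these provisions sets a time at which participants are asked about symptoms after stimulation, and the section that should set one is NA.

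**Conclusion.** The point holds in a limited form. The plan specifies no systematic collection of headache, neck or scalp pain, or hearing symptoms at the end of a TMS visit or for the interval between visits. Mild symptoms, and those that resolve the same day, may therefore be under-counted. Severe or persisting ones have a reasonable chance of being noticed.

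The extent of the under-count cannot be derived from the documents. The pool is small if the quoted theta-burst ceiling applies to this study: at most about 2.4 of 80 or 4.5 of 150 participants on a per-person reading, and about 12 events in 80 participants on a per-session reading over five sessions. The figures depend on that ceiling, on its unstated denominator and on which sample size is meant. The conclusion that later symptoms are not systematically asked about does not depend on them. The consequence is an incomplete safety record; no planned efficacy analysis is affected. The change is worth making because it is cheap and the study repeats stimulation in every participant.

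**What to change.** Four changes, all to data collection:

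1. Section 10.1: reword the repeat TMS screen so that it asks about changes since the last screening. Add yes/no items on headache, neck or scalp pain, and hearing change or tinnitus since the last TMS session.
2. Section 6.2: give the listed pain scale at the end of each TMS visit, after the tasks, and state its recall period.
3. Ask the same items once after the final TMS session, at the next scheduled visit or by the e-mail route already used for screening.
4. Record each event by stimulation site and by onset during or after stimulation, and enter these arrangements in section 18.1 in place of NA.

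The cost is a few items on a form already completed each session, a set time for a scale already listed, and at most one e-mail per participant. The recorded adverse-event rate may look less favourable.

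Separately, section 15.1 says in one place that the procedure ends when discomfort is reported (as does 6.3), and in another that intensity is lowered if stimulation is painful. These passages must be reconciled.

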TMS will be delivered to multiple sites of interest. Site order will be randomized across participants.

Electroencephalography (EEG) will be used to measure changes in brain activity caused by TMS. The EEG assesses electrical brain activity through surface recording disks (electrodes) which are placed near the participant's head. The electrodes transmit the signals, which are then amplified (via an 8 channel Brain Vision

LiveAmp) and stored on a computer. The procedure is entirely non-invasive.

An electrode cap will be placed on the participant's head. In order to record brain activity, these disks need to be filled with a gel which allows the electrodes to better record brain activity at the scalp. Therefore, the participants in this study will need to clean their hair after participation. The gel is completely water soluble, and the procedure is painless. The MRI facility has sinks and towels, and the investigators will help to make sure the participant has thoroughly rinsed all the gel from their hair. After an accurate signal is assured, the signal derived from the electrode cap is then amplified, transmitted to a computer, and stored for later analysis. In addition to the EEG recording, muscle activity from around the eyes may be recorded from the subjects. Muscle activity from around the eyes is recorded by two small sensors that will be placed below the participant's left eye, as well as behind the ears. These procedures are completely noninvasive and painless.

*6.2 Provide a description of all research procedures being performed and when they are performed, including procedures being performed to monitor subjects for safety or minimize risks.*

Below is a description of the kinds of tasks that participants will perform. In general, tasks will range in duration from 5-10 minutes to 1-2 hours. Breaks will be given every 5-10 minutes. Multiple sessions may be performed. Based upon performance on the tasks, we may contact participants to perform other related tasks. Returning to perform other tasks will be optional and have no bearing upon the tasks the participants have already completed.

- Computer-based Tasks
  - Doors Task

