    - a. Participants will be shown graphics depicting doors, and will be asked to choose a door. After picking a door, participants receive feedback on the screen indicating whether they have won or lost on that trial. The participants' goal is to do their best to win as much money as possible. In this task, participants will receive a monetary bonus for correct guesses, which will total between \$0.00 and \$10.00 depending on how many correct guesses they make. This task will take approximately 5-10 minutes.
  - Motivated Behavior Task

- a. Participants will be given the opportunity to complete a specified number of trials for a specified reward. Trials will entail trials of the tasks described above or other simple cognitive tasks such as arithmetic.
- Written tasks
  - DARS
    - a. Self-reported anhedonia will be measured using the Dimensional Anhedonia Rating Scale (DARS). The DARS is an appealing measure due to its high internal consistency, convergent validity with other measures of anhedonia, divergent validity with depression scores, and ability to capture state levels of anhedonia. This latter property makes it suitable for measuring changes in anhedonia.
  - Screening
    - a. Participants will be screened to be fluent in English, between the ages of 18-55, and to have no contraindications for MRI or TMS. Participants will also be screened such that they do not belong to populations vulnerable to the Coronavirus Disease (COVID-19), and have not been exposed. To be eligible for participation in this study, participants must score 46 or below on the DARS, reflecting increased anhedonia.
  - Demographics
    - a. Demographic information including age, gender, race, and ethnicity will be collected. This information will be used for reporting purposes to demonstrate fair inclusion. Participants will be informed that providing this information will be optional. This information has no direct bearing upon the research to be performed
  - Handedness
    - a. Edinburgh Handedness Inventory, which asks about which hand is used in various tasks, will be collected to determine the dominant hand.

- DSM Crosscutting
  - a. The DSM-5 Level 1 Cross-Cutting Symptom Measure is a self- or informant-rated measure that assesses mental health domains that are important across psychiatric diagnoses.
- World Health Organization Disability Assessment Schedule (WHODAS)

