## 9.0 Study Timelines\*

### 9.1 Describe:

- *The duration of an individual subject's participation in the study.*
- *The duration anticipated to enroll all study subjects.*
- *The estimated date for the investigators to complete this study (complete primary analyses)*

The duration for each individual's participation will be between 30 minutes and 2 hours per session. Participants will participate in at least 1, and potentially several sessions. It may take up to several weeks to complete an entire task. The duration anticipated to enroll all study subjects is 72 months.

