Transient cognitive/neuropsychological changes. Some repetitive TMS protocols have been shown to affect cognitive processing for up to one hour following stimulation. Specifically, this is the case for "offline" techniques such as 1 Hz stimulation and theta-burst stimulation (TBS; Huang et al., 2005). These changes are small, but could in theory affect the subject's ability to drive home safely. However, our use of offline TMS always precedes the actual experimental task that subjects are performing. Since the effects of the TMS parameters we are proposing to use have never been observed to last more than 1 hour, the potential cognitive effects of TMS are

expected to have worn off by the time the testing session is concluded. Participants may experience frustration from poor performance on the task. Another potential risk is probing for personal or sensitive information in surveys, interviews, or questionnaire.

Although we do not expect it to occur frequently, some subjects may endorse suicidality or increased risk for suicidality; in this event, we will implement the following protocol:

Participants will have a clinical interview performed, and as part of that clinical interview, we will assess suicidality. If participants endorse any suicidal ideation, the severity of suicidality will be assessed using the structured interview on the following pages, and the Joiner method. This procedure is adopted from the FSU Psychology Clinic using the clinic's suicide decision tree, which is an empirically validated structured interview.

Joiner et al. (1999) use the following method to designate risk severity:

1. An individual's risk for suicide is designated nonexistent if he or she has no current suicidal symptoms, no history of suicide, and no or few other risk factors.
2. Risk for suicide is considered mild if the individual is a multiple attempter with no other risk factors or is a non-multiple attempter experiencing suicidal ideation of limited intensity and duration, no or mild Resolved Plans and Preparation, and no or few other risk factors.
3. An individual is designated at moderate risk if he or she is a multiple attempter with any other significant risk factor. A non-multiple attempter with moderate to severe Resolved Plans and Preparations or moderate to severe Suicidal Desire and Ideation accompanied by at least two other risk factors is also considered to be at moderate risk for suicide.

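### Section 15.1 answers its driving concern by expecting TMS effects to wear off by session end, but the visible text does not secure the one hour this needs

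*Combined protocol and SAP*

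**What the plan says.** Under transient cognitive changes, section 15.1 says that some repetitive TMS protocols, TBS among them, have been shown to "affect cognitive processing for up to one hour following stimulation". On the consequence it says "These changes are small, but could in theory affect" the participant's ability to drive home safely.

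Its answer has two parts. The first is sequence: "our use of offline TMS always precedes the actual experimental task that subjects are performing". The second is duration: the effects of the proposed parameters "have never been observed to last more than 1 hour". From these it concludes that the effects are "expected to have worn off by the time the testing session is concluded".

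Other sections bear on the time available:

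- Section 9.1 gives participation as "between 30 minutes and 2 hours per session", with no separate figure for stimulation visits.
- Section 6.2 says "tasks will range in duration from 5-10 minutes to 1-2 hours", and of the Doors Task: "This task will take approximately 5-10 minutes".
- Section 19.2 lets participants stop or leave whenever they wish.
- Sections 6.3 and 15.1 end the procedure at once if discomfort is reported, and give no release time.
- Section 2.2 plans five TMS sessions within a week. No visible section says which task follows each one.

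**The concern.** The conclusion in section 15.1 needs about 60 minutes between the last pulse and departure. The premise offered is only that stimulation comes before the task. A task of an hour or more would supply the interval; a 5-minute task would not. The visible text allows both.

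What is at stake is participant safety, not inference. If a stimulation visit is short, or a participant leaves early, staff who follow section 15.1 as written could release someone to drive inside the window that the protocol itself names.

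**Working it through.** **Inputs**

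- Window: 60 minutes, the protocol's own upper bound (15.1).
- Shortest session: 30 minutes (9.1).
- Intermittent TBS: 190 s, or 3.17 min (stated in 6.1). As a check, 600 pulses at 3 per burst is 200 bursts. At 5 bursts per second, a 2-second train holds 10 bursts, so there are 20 trains. 20 × 2 s + 19 × 8 s = 192 s, in line with the stated 190 s.
- Continuous TBS: not stated. Derived from 6.1 as 600 / 3 / 5 = 40 s = 0.67 min.
- Motor threshold: about 5 minutes (6.1), or 0 if it is not repeated at that visit.
- Doors Task: 5 to 10 minutes (6.2).

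**Case A: a 30-minute stimulation visit (assumed)**

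Most time after the last pulse = 30 − threshold − TBS. Least part of the window falling after departure = 60 − that time.

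| Steps up to the last pulse | Minutes used | Most time left in the visit | Least part of the window after departure |
|---|---|---|---|
| Continuous TBS, no threshold | 0.67 | 29.3 | 30.7 |
| Intermittent TBS, no threshold | 3.17 | 26.8 | 33.2 |
| Threshold + continuous TBS | 5.67 | 24.3 | 35.7 |
| Threshold + intermittent TBS | 8.17 | 21.8 | 38.2 |

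The last column is a lower bound. TMS re-screening at each session (10.1) and any other set-up before stimulation have no stated duration. They reduce the time after the last pulse further.

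**Could such a visit fit in 30 minutes?**

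Threshold + TBS + Doors Task runs from 0 + 0.67 + 5 = 5.7 min to 5 + 3.17 + 10 = 18.2 min. That leaves 30 − 18.2 = 11.8 to 30 − 5.7 = 24.3 min for re-screening, EEG set-up, rinsing and any questionnaires. It is possible on paper, but the documents do not give the durations that would settle it.

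**Case B: only the Doors Task follows the last pulse**

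Remaining window = 60 − 10 = 50 min to 60 − 5 = 55 min. These are maxima. Section 6.1 describes a gel cap, signal checks and help with rinsing the hair. Any of these done after the last pulse reduces what remains.

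**Visit length that would cover the hour**

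60 + 0.67 = 60.7 min (continuous TBS, no threshold) to 60 + 5 + 3.17 = 68.2 min (threshold and intermittent TBS), plus any set-up before stimulation. The upper part of the 30-to-120-minute range therefore covers the window if stimulation comes early in the visit; the lower part does not.

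**The case against.** The strongest reply is that the material most likely to hold a driving instruction was not available. Section 23.3 says a consent document is attached, and the protocol also refers to appendices. A reader might infer that the study gives participants no advice about driving. The documents do not support that inference, because pages removed from the review copy are not missing from the plan. What stands is narrower: section 15.1 makes its own argument, cites no such instruction, and rests on session timing alone.

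Second, the 30-minute range in section 9.1 is general text covering every kind of session, possibly including interviews and questionnaires. A reader might infer that 30-minute stimulation visits are planned. Nothing shows that. Visits with EEG or fMRI after stimulation may well exceed an hour. This stands, and it is why Case A is labelled an assumption.

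Third, ending the procedure for discomfort is not the same as sending the participant home, and a stop during stimulation means fewer pulses. The right to leave is also a proper safeguard, not a flaw. Both points are fair. Even so, a participant may leave soon after a full course of pulses however long the visit was meant to be, and the timing argument does not cover that.

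Finally, the protocol calls the changes small and the driving risk theoretical. One hour is the longest duration it reports, not a typical one. This is accepted and sets the severity.

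**Conclusion.** The point holds in a limited form. The visible text does not secure the hour on which section 15.1 depends, because it gives an order of events and no minimum interval after the last pulse.

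The size is conditional. In an assumed 30-minute stimulation visit, at least 30.7 to 38.2 minutes of the window would fall after departure. With the Doors Task alone after stimulation, at most 50 to 55 minutes would remain, before any time for EEG set-up after TMS, cap removal and rinsing. Visits with an hour or more of tasks after the last pulse already cover the window.

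The documents do not show that anyone will drive while affected; they show only that the stated reasoning does not rule it out. Severity is low, and no endpoint or estimate is affected.

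**What to change.** In section 15.1 and the participant instructions, advise participants at every stimulation visit not to drive until 60 minutes after the last pulse. State that this also applies after an early stop or an early departure. Offer a place to wait on site but do not require its use, since a compulsory wait would conflict with the right to leave in section 19.2. If the consent form already gives this advice, cite it in section 15.1 in place of the session-timing argument.

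Timing the advice from the last pulse rather than from visit length means that section 9.1 needs no change.

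The cost is one or two sentences, or one cross-reference. Some participants would wait or arrange other transport. The wait is at most 60 minutes per stimulation visit, and none where later tasks already fill the hour.
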